9.2.3 Study Time Periods

The overall **study period** is from 2010 through 2020. Different start dates are defined based on which two drugs are compared and, for the comparison with rhFSH-alfa biosimilar products, which country is analyzed. The study period ends on 31 December 2020 (or last available data) for both study drug comparisons and countries. Homogeneity in patient management over time, market entry of the comparator drugs and register lag times determine the start and end dates of the study period:

- rhFSH-alfa reference product vs. HP-hMG:
 - o Denmark, Sweden: 1 January 2010 – 31 December 2020
- rhFSH-alfa reference product vs. rhFSH-alfa biosimilar products:
 - o Denmark: 26 March 2014 – 31 December 2020
 - o Sweden: 20 June 2014 – 31 December 2020

For Sweden, inclusion of eligible women may need to be restricted to 31 December 2019, considering study timelines (see Section 6) and the typical two-year lag time for data availability from the Swedish National Quality Registry of Assisted Reproduction (Q-IVF) (see Section 9.4.2).

The overall **index date** is the date when the woman's *first* eligible IVF/ICSI stimulation cycle started (defined as start of ovarian stimulation) in the study period. The **stimulation cycle index date** is the date when each stimulation cycle started. For FET cycles linked to an included stimulation cycle, the cycle start date is the Last Menstrual Period (LMP) date for natural FET cycles or the date hormonal stimulation (replacement) treatment was started for stimulated FET cycles, as recorded in each country's IVF register.

The **baseline period** is defined as the 36-month minimum period prior to and including the (stimulation cycle) index date. During this period, (cycle) eligibility will be determined, and baseline covariates assessed. The baseline period may include time before the age of 18 years, for women who had IVF/ICSI treatment specifically at the age of 18 years. All available data from the registers will be used to obtain information on important covariates. Baseline data from the national patient registers, however, will be limited to the period in which ICD-10 coding has been

used comprehensively in each country (starting from 1994 in Denmark and 1998 in Sweden). The exact length of the baseline period will therefore vary between cycles within the same patient.

The overall **follow-up period** among women included in the study is the time between the index date and the exit date. The exit date is the censoring date, as defined according to the following general censoring criteria: initiation of a sixth stimulation cycle (regardless of gonadotropin used for COS), end of the study period, emigration (available for Denmark only), death, hysterectomy, bilateral oophorectomy or diagnosis of breast, ovarian or uterine cancer, whichever occurs first. Moreover, each included stimulation cycle will be followed from the stimulation cycle index date until the date when each outcome is assessed; this date varies between the analyses of different objectives and outcomes (see Section 9.7). For a graphical illustration of the study time periods, see Figure 1. As applicable, diagnosis and procedure codes used to define the censoring criteria are provided in Appendix 3 (Section 14.3.2).

9.3 Variables

Derived and transformed data needed for the analysis are described in Section 9.7.2.

9.3.1 Exposure Variables

Exposure of an IVF/ICSI stimulation cycle to rhFSH-alfa reference product (follitropin alfa, ATC code G03GA05), HP-hMG (ATC code G03GA02) or rhFSH-alfa biosimilar product (ATC code G03GA05) will be established based on information from the IVF registers and, primarily, prescriptions dispensed in community pharmacies. While the IVF registers indicate which drug (international nonproprietary name (INN)/ATC) was used for ovarian stimulation, the prescribed drug registers comprise more detail. Additionally, in Sweden, drug information is expected to be available from the Q-IVF starting only from 2019.

Hence, information on the dispensed prescription will include substance name (INN), brand name, ATC code, strength of drug, dosage form, pack size, number of dispensed packages and dispensed amount of drug [in Defined Daily Doses (DDD)]. Using the brand name recorded with the dispensed prescription, it will be possible to distinguish between rhFSH-alfa reference product and rhFSH-alfa biosimilar product. Because information on prescribed daily dose is expected to be incomplete and/or recorded in free-text format, it will not be considered for estimation of total gonadotropin dose.

Using data from the prescribed drug registers, a time window of 30 days before and 35 days after the stimulation cycle index date (27) will be defined to ascertain that gonadotropin monotherapy with a study drug was used for COS. The impact of using a narrower time window for exposure ascertainment will be explored in a sensitivity analysis (see Analysis 1 in Table 8). Any FET cycle(s) linked to an IVF/ICSI stimulation cycle included in the study will be considered exposed to the same study drug as the cycle it originated from.

Total gonadotropin dose will not be considered in the analyses of the comparative study objectives (1-8). However, conditional that the data from the Q-IVF is comprehensive, total gonadotropin dose may be considered for the estimation of drug cost in the descriptive cost analysis for Sweden (see Section 9.7.3.7), albeit for a limited portion of the study period.

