9.2.2 Definition of Study Cohorts and Description of Treatments

Among the women included in the study, three study cohorts will be created at the level of the IVF/ICSI stimulation cycle based on which drug the woman received for COS: rhFSH-alfa reference product, HP-hMG or rhFSH-alfa biosimilar product. Only one type of gonadotropin use will be allowed for each stimulation cycle. Hence, cycles where mixed gonadotropin use was observed will not be included in the study. Mixed gonadotropin use may occur for example if, at prescription refill at the pharmacy, the drug (brand) on the written prescription was exchanged for an equivalent drug (same active substance, strength, formulation; therapeutically equipotent).

A woman may contribute maximum five stimulation cycles to the same cohort if she had several cycles with the same study drug. She may contribute cycles to more than one study cohort if she had distinct stimulation cycles with different study drugs. Between stimulation cycles with a study drug, a woman may have received a non-study gonadotropin for COS. History of IVF/ICSI treatment, including with a non-study gonadotropin, will be controlled for in the analysis (in the PS estimation). Overall, no more than five stimulation cycles and only up to the fifth stimulation cycle will be considered in this study, regardless if all cycles were observed in the study period and the type of gonadotropin used for COS.

FET cycles originated from an IVF/ICSI stimulation cycle included in the study will be assigned to the same cohort as that stimulation cycle. FET cycles originated from a stimulation cycle in which one of the study drugs was used but which was not included in the study (e.g., because of PGT), will not be considered. Different methods for cycle linkage will be used for Denmark and Sweden. For Sweden, the IVF register includes information enabling an FET cycle to be linked to the stimulation cycle it originated from. This information is the follicular aspiration date, which is recorded for IVF/ICSI stimulation cycles and FET cycles alike. For Denmark, no such direct link exists in the IVF register.

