9.7.3.9 Sensitivity Analyses

Sensitivity analyses will be performed as outlined below for the primary study objective and, in one analysis (no. 3), for secondary objective 4 (Table 8).

Table 8. Overview of sensitivity analyses

No.	Topic	Main analysis		Sensitivity analysis	
		Method	Justification	Alteration to method	Justification
1	Time window for establishing stimulation cycle exposure to study drug	30 days before to 35 days after stimulation cycle index date	The IVF registers do not capture drug data comprehensively. To establish exposure of a stimulation cycle to a study drug, and one study drug only, data on dispensed prescriptions for gonadotropins are ascertained from the prescribed drug registers. A time window has been defined to capture all relevant dispensed prescriptions for gonadotropins in each cycle.	15 days before to 15 days after stimulation cycle index date	The time window for exposure establishment used in the main analysis has only been used in one prior study (27) to our knowledge. The effect of choosing a narrower time window will be explored for the primary objective and each associated outcome measure (LBR, CLBR, MC-CLBR). Otherwise the analysis will be repeated as described in 9.7.3.3 and 9.7.3.4.
2	Approach for estimation of MC-CLBR	The main analysis uses a conservative approach to estimating the MC-CLBR. It assumes none of the women who did not return for a subsequent cycle would have had a live birth, had they returned (20).	Discontinuation of IVF/ICSI treatment, i.e. , not returning for treatment after a failed attempt (live birth was not achieved) needs to be considered in the analysis of cumulative live birth rates assessed over multiple stimulation cycles.	Optimal approach to estimating the MC-CLBR. It is based on the observed data and assumes women who did not return for a subsequent cycle would have had the same live birth rates as those who did return (20).	The true MC-CLBR is thought to lie between the conservative and optimal estimates (39). Calculating both estimates will provide the range in which the actual value would be expected to fall. The analysis of MC-CLBR will otherwise be repeated as described in 9.7.3.3 and 9.7.3.4.

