9.9 Limitations of the Research Methods

9.9.1 Selection Bias

Owing to the use of secondary data originally collected for purposes unrelated to this study, biased results arising from how women are selected into the study is considered a minor issue. Selection will not depend on both exposure status and risk factors for the outcomes, which can otherwise lead to biased exposure-outcome associations. Moreover, all registers used in the study have nationwide coverage and employ mandatory reporting for publicly- and privately-operated units. The Swedish IVF register is an exception as being a quality register, to which reporting is not mandatory; however, close to 100% of all IVF clinics in Sweden report data to the register (33).

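### Cohort entry depends on gonadotropin dispensings up to 35 days after stimulation start, so the monotherapy rule can remove cycles for reasons related to how they went

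*Protocol*

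**What the plan says.** Inclusion criterion 1 in Protocol 9.2.1 requires monotherapy with one study drug. Section 9.3.1 says how this is established from the prescription registers: "a time window of 30 days before and 35 days after the stimulation cycle index date (27) will be defined", the purpose being "to ascertain that gonadotropin monotherapy with a study drug was used for COS". Section 9.2.2 gives the consequence of seeing a second product: "cycles where mixed gonadotropin use was observed will not be included in the study". Its one example of how this arises is that "at prescription refill at the pharmacy, the drug (brand) on the written prescription was exchanged for an equivalent drug".

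The end of 9.2.2 says a cycle needs only to have been started, not to have reached embryo transfer, in order to count. Table 7 in 9.7.3.3 uses initiated cycles as the denominator for LBR and CLBR.

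On bias, 9.9.1 states: "Selection will not depend on both exposure status and risk factors for the outcomes". Section 9.9.2 discusses the length of the window only as a source of misclassified or missed exposure. Sensitivity Analysis 1 (Table 8, 9.7.3.9) narrows the window to "15 days before to 15 days after stimulation cycle index date" for LBR, CLBR and MC-CLBR.

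**The concern.** Time zero is the start of stimulation, yet eligibility is settled only on day 35. There are two routes by which the course of the cycle can decide whether it stays in.

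- **Within the cycle.** A woman who needs a refill and receives another brand, or who has a second product added, becomes mixed. Refills are more likely when stimulation is longer or heavier.
- **Next attempt.** A woman whose cycle is cancelled or fails, and who collects a different product by day 35, can make the cycle just ended look mixed. A woman who has conceived has no next stimulation to collect for.

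Both routes remove started cycles from measures meant to count every started cycle. The second also sits badly with 9.7.3.5, where time-to-live-birth follow-up ends at a switch of drug: on that logic the cycle before the switch is an observed failure, not one to be erased. Weighting on baseline covariates cannot bring back cycles removed for what happened after baseline. At stake are the absolute rates and, if products differ in how often users are switched or supplemented after a poor course, the comparison itself.

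**Working it through.** The documents give no count of mixed-use cycles and no deletion share, so there is no stated figure to reproduce. The check has two parts.

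**1. Reach of the window.** If the next stimulation starts on day d, its own window runs from d − 30 to d + 35. It overlaps the earlier window (−30 to +35) when d − 30 ≤ 35, that is, d ≤ 65. A product collected for a cycle starting as late as day 65 can therefore fall inside the earlier cycle's window. Under Analysis 1 the condition is d − 15 ≤ 15, so d ≤ 30. That analysis ignores days 16 to 35, where most early restarts would be expected, but still counts product changes on days 1 to 15.

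**2. Effect of deletion on the results.** Let p be the true live birth rate, equal in cohorts A and B. Let x be the share of failed cycles deleted and y the share of successful cycles deleted.

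- Observed rate = p(1 − y) / [p(1 − y) + (1 − p)(1 − x)]
- Spurious OR, A versus B = [(1 − yA)(1 − xB)] / [(1 − xA)(1 − yB)], whatever p is

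All shares below, and p = 25%, are assumptions.

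| xA / xB | yA / yB | Observed A vs B | OR |
|---|---|---|---|
| 5% / 5% | 0 / 0 | 26.0% vs 26.0% | 0.95/0.95 = 1.00 |
| 5% / 2% | 0 / 0 | 26.0% vs 25.4% | 0.98/0.95 = 1.03 |
| 10% / 3% | 0 / 0 | 27.0% vs 25.6% | 0.97/0.90 = 1.08 |
| 3% / 8% | 0 / 0 | 25.6% vs 26.6% | 0.92/0.97 = 0.95 |
| 10% / 3% | 5% / 1.5% | 26.0% vs 25.3% | (0.95 × 0.97)/(0.90 × 0.985) = 1.04 |
| 10% / 3% | 10% / 3% | 25.0% vs 25.0% | 1.00 |

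Equal deletion of failures inflates both rates but leaves the OR at 1. Unequal deletion moves the OR in either direction. Deleting successes at half the rate of failures roughly halves the bias, and deleting them at the same rate removes it.

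**The case against.** The other side has several good points.

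- **Successes are lost too.** A reader might infer that failed cycles are deleted while successful ones are always kept. The text does not support that. A brand exchange at refill happens before the outcome is known, so it also removes cycles that go on to a live birth. Retention of successes is a tendency only. This stands, and it is why the failures-only rows are an upper illustration.
- **The next-attempt route is a reading of the rule.** Section 9.2.2 lets a woman contribute distinct cycles on different study drugs to more than one cohort, so consecutive cycles on different products are meant to be usable. Allocating a dispensing to the right cycle could be SAP detail. But 9.3.1 as written has no such carve-out, and 9.9.2 accepts that a long interval can attribute prescriptions to the wrong cycle. Overlapping windows can remove both cycles; nothing shows that they must.
- **Analysis 1 is a real mitigation.** It removes much of the next-attempt route. It leaves changes during the first 15 days, does not alter the main estimate, and covers only the primary objective. Cycle cancellation and oocyte yield, which are directly exposed, get no such check.
- **The only example given is an exchange within one active substance.** That bears on reference versus biosimilar. The documents do not say that products are switched for poor response, or that this differs by product. This stands: differential loss is plausible but not shown.
- **The size benchmark does not transfer.** At a 50% rate, deleting 5.8% of failures in one cohort alone gives 0.50/(0.50 + 0.50 × 0.942) = 51.5%. A reader might infer that this alone produces the 1.5-point difference in 9.5. That figure is for the HP-hMG comparison and uses MC-CLBR per woman; the biosimilar figures are 2.0 and 2.5 points. A per-cycle share carries over only if losing a first cycle removes the woman, which the text does not settle.
- **Classifying at day 0 changes the question** from monotherapy to product as started. This is a fair argument about which analysis should be the main one, but not against having both.

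**Conclusion.** The concern holds in a limited form. Sections 9.2.1, 9.2.2 and 9.3.1 together make cohort entry depend on events after time zero, and the cycles removed will tend to be those with a poor course. The assurance in 9.9.1 is therefore too absolute, and 9.9.2 does not recognise the selection.

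Absolute rates per initiated cycle are inflated wherever failures are removed more often than successes. The OR is biased only if that imbalance differs between products. Neither size nor direction can be derived from the documents. Under assumed failure-only deletion the spurious OR is 1.03 (5% versus 2%) to 1.08 (10% versus 3%), could equally fall below 1, and shrinks as successes are deleted too. With cohorts of this size, an effect of that order is not negligible beside the differences the study hopes to show.

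**What to change.** - In 9.3.1 and Table 8, add a prespecified analysis that assigns each cycle to the product dispensed in the window closing at the stimulation cycle index date, and keeps cycles with a later change in the cohort they started in. Preferably make this the main analysis and run the −30/+35 monotherapy rule as the sensitivity analysis.
- Apply it to cycle cancellation and oocyte yield as well as the primary measures.
- State that a dispensing belonging to a subsequent recorded cycle does not disqualify the earlier one.
- Report the number of cycles removed by the mixed-use rule, by cohort and by cycle outcome. This would show whether the loss is differential.
- Correct 9.9.1, and add to 9.9.2 that the window also acts as a selection rule.

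The cost is protocol and SAP wording plus one reprogrammed exposure rule on data already planned for extraction. The downside is that some mixed exposure stays in the cohorts and may dilute a true difference, and cycles whose first dispensing falls after day 0 are lost from that analysis. The change should be settled before results are seen.

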9.3.2 Other Variables (Covariates)

In addition to the outcome and exposure variables outlined in Section 9.1.2 and Section 9.3.1, the covariates of interest in this study are listed below and classified according to their intended use in the analysis (Table 1).

The variables are generally described as measured in relation to each IVF/ICSI stimulation cycle; however, variables used to derive the outcome variables may also apply to any linked FET cycles, depending on the outcome under study. Variables indicated as being candidates for regression modeling are determined after the decision on which gonadotropin to use for COS has been made. These variables will therefore not be included in the PS but may instead be added as independent covariates in the IPTW-weighted regression model (see Section 9.7.3.1 for further details).

For variables identified in the registers by ATC, ICD-10 and/or procedure codes, these operational definitions are provided in Appendix 3 (Section 14.3.3).

Table 1. List of covariates and their use in the study

Variable	Measurement scale	Baseline characteristic	Candidate variable for PS	Candidate variable for additional adjustment
Demographic characteristics				
Age at stimulation cycle index date	Continuous	X	X	
IVF/ICSI treatment characteristics				
Treatment type (ICSI, IVF, ICSI + IVF; FET)	Categorical	X	X	
Type of clinic (private, public)	Categorical	X	X	
Calendar year of stimulation cycle	Continuous	X		
GnRH protocol (agonist, antagonist)	Categorical	X	X	
Cycle cancellation (timing within cycle)	Categorical	N/A (used to derive outcome variable)		
Date of cycle cancellation	Continuous	N/A (used to derive outcome variable)		
Type of drug for ovulation triggering	Categorical	X		X

Variable	Measurement scale	Baseline characteristic	Candidate variable for PS	Candidate variable for additional adjustment
Type of drug for luteal phase support	Categorical	X		X
Date of follicular aspiration	Continuous	N/A (used to derive outcome variable)		
Date of embryo transfer	Continuous	N/A (used to derive outcome variable)		
Number of days of embryo cultivation ⁺	Numerical	X		X
Date of embryo cryopreservation	Continuous	N/A (used to derive outcome variable)		
Embryo cryopreservation method (slow freezing, vitrification)	Categorical	X		X
Date of embryo thawing	Continuous	N/A (used to derive outcome variable)		
Number of embryos thawed	Continuous	N/A (used to derive outcome variable)		
Date of pregnancy test	Continuous	N/A (used to derive outcome variable)		
Pregnancy test result or indicator for pregnancy	Continuous	N/A (used to derive outcome variable)		
Date of ultrasound	Continuous	N/A (used to derive outcome variable)		
Date of pregnancy loss	Continuous	N/A (used to derive outcome variable)		
Other clinical characteristics				
Height/weight or BMI	Continuous	X	X	
Obesity	Categorical	X	X	
Bariatric surgery	Categorical	X	X	
Smoking status*	Numerical	X	X	

Variable	Measurement scale	Baseline characteristic	Candidate variable for PS	Candidate variable for additional adjustment
Type 1 diabetes mellitus	Categorical	X	X	
Type 2 diabetes mellitus	Categorical	X	X	
Antidiabetic drugs	Categorical	X	X	
History of thromboembolic events	Categorical	X	X	
Use of thrombosis prophylaxis	Categorical	X	X	
Porphyria and other relevant conditions [#]	Categorical	X	X	
History of any cancer	Categorical	X	X	
Medical history, fertility-related				
Number of previous failed COS	Categorical	X	X	
History of failed IUI	Categorical	X	X	
History of COS with a study drug	Categorical	X	X	
History of COS with a non-study drug	Categorical	X	X	
Previous delivery with at least one live birth following IVF	Categorical	X	X	
Parity	Categorical	X	X	
OHSS	Categorical	X	X	
Amenorrhea or oligomenorrhea	Categorical	X	X	
PCOS	Categorical	X	X	
Endometriosis	Categorical	X	X	

Variable	Measurement scale	Baseline characteristic	Candidate variable for PS	Candidate variable for additional adjustment
Female infertility diagnosis	Categorical	X	X	
Female factor infertility*	Categorical	X	X	
Male factor infertility*	Categorical	X	X	
Idiopathic factor infertility*	Categorical	X	X	
Medical history, laboratory test results (value at most recent record on or prior to stimulation cycle index date) [†]				
Anti-Müllerian hormone, pmol/L	Continuous	X	X	
FSH, IU/L	Continuous	X	X	
Thyrotropin, mIU/L	Continuous	X	X	
Prolactin, mIU/L	Continuous	X	X	

BMI: body mass index; COS: controlled ovarian stimulation; FET: frozen embryo transfer; FSH: follicle-stimulating hormone; GnRH: gonadotropin-releasing hormone; ICSI: intracytoplasmic sperm injection; IUI: intrauterine insemination; IVF: in vitro fertilization; IU: international unit; L: liter; mIU: milli-international unit; OHSS: ovarian hyperstimulation syndrome; PCOS: polycystic ovarian syndrome; pmol: picomole; PS: propensity score.

Notes:

[†]Not available in Denmark and available from 2015 in Sweden; can be approximated by subtracting the date of follicular aspiration from the date of embryo transfer for stimulation cycles.

* Available for Denmark only (from the DIVF).

Full list of conditions to be considered is provided in Appendix 3 (Section 14.3.3).

[‡] Available for Denmark only [from the Danish Register of Laboratory Results for Research (RLRR); see Section 9.4.1]. Because completeness is uncertain, these data will be used in a sensitivity analysis only, as described in analysis 4 in Table 8.

